Investigational medicinal products

Cetuximab

Cetuximab will be administered [REDACTED] [REDACTED].

- Formulation:
 - a clear, colorless solution for injection provided as 100 mg/50 mL (2 mg/mL) or 200 mg/100 mL in a single-dose vial
 - or*
 - 100 mg/20 mL or 500 mg/100 mL
 - or*
 - any other cetuximab formulation approved locally.
- Route of administration: IV infusion

Dose regimen: Cetuximab will be given on Cycle 1 Day 1 as an initial loading dose of 400 mg/m² infused over 120 minutes (maximum infusion rate 10 mg/min, or as per local practice and labels) followed by 250 mg/m² infused over 60 minutes (maximum infusion rate 10 mg/min) for all subsequent doses starting with the Cycle 1 Day 8 administration, until PD.

Noninvestigational medicinal products

Premedication for SAR444245 as described in the master protocol.

Premedication for cetuximab

All participants who will receive cetuximab should be premedicated with diphenhydramine 25 to 50 mg IV (or equivalent) prior to the first dose of cetuximab or any other recommended premedication as per local requirements. Premedication for subsequent doses of cetuximab should be given per medical judgment and history of prior infusion reactions (IRs).

Each dose of cetuximab will be followed by a 1-2 hours observation period. If there are no reported infusion-related reactions (IRRs) during this observation period, then the SAR444245 dose may be administered at applicable dosing visits.

When SAR444245 and cetuximab are given on the same day, participants who have received diphenhydramine as cetuximab premedication may skip the diphenhydramine as SAR444245 premedication.

Statistical considerations:

[figure not shown]
Please refer to the master protocol for description of common statistical considerations. Substudy-specific analyses are summarized below.

- Active concentrations of cetuximab when given in combination with SAR444245 will be analyzed with descriptive statistics.

Data Monitoring/Other committee: Yes

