2.3.1.2 Cetuximab

The important identified risks for cetuximab include, but are not limited to: infusion reactions (including anaphylaxis on the first dose); interstitial lung disease, severe adverse skin reactions (with increased risk of secondary bacterial infection), electrolyte disturbances (hypomagnesemia, hypokalemia, hypocalcemia) cardiac adverse events (including cardiopulmonary arrest/sudden death), and eye disorders (including ulcerative keratitis).

The most common adverse reactions (incidence $\geq 25\%$) are: cutaneous adverse reactions (including rash, pruritus, and nail changes), headache, diarrhea, and infection.

The following precautions and warnings are to be acknowledged:

Cetuximab can cause serious and fatal infusion reactions. Infusion reactions of any grade occurred in 8.4% of patients who received cetuximab across clinical trials. Grades 3 and 4 infusion reactions occurred in 2.2% of patients. Signs and symptoms included rapid onset of airway obstruction (bronchospasm, stridor, hoarseness), hypotension, shock, loss of consciousness, myocardial infarction, and/or cardiac arrest. The risk of anaphylactic reactions may be increased in patients with a history of tick bites, red meat allergy, or in the presence of IgE antibodies directed against galactose- α -1,3-galactose. Approximately 90% of severe infusion reactions occurred with the first infusion despite premedication with antihistamines. Infusion reactions may occur during or several hours following completion of the infusion. Premedication with a histamine-1 (H1) receptor antagonist is recommended together with monitor patients for at least 1 hour following each infusion.

Cardiopulmonary arrest or sudden death have occurred in 2-3% patients with squamous cell carcinoma of the head and neck receiving cetuximab with radiation therapy or a cetuximab product with platinum-based therapy and fluorouracil. A history of coronary artery disease, congestive heart failure, or arrhythmias and abnormal serum electrolytes may be predisposing factors.

Interstitial lung disease (ILD) that may be fatal has occurred in $<0.5\%$ of patients receiving cetuximab in clinical trials.

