Grade 3 Prolonged (ie, not rapidly responsive to symptomatic medication and/or brief interruption of infusion); recurrence of symptoms following initial improvement; hospitalization indicated for other clinical sequelae	SAR444245 infusion should be interrupted if applicable. If IRR is clearly attributable to SAR444245, SAR444245 should be permanently discontinued. The participant can continue treatment with the other anti-cancer therapy in combination During or after completion of infusion, additional appropriate medical therapy may include but is not limited to epinephrine ^b , IV fluids, antihistamines, NSAIDs, acetaminophen, narcotics, oxygen, vasopressors, corticosteroids. Increase monitoring of vital signs as medically indicated until the participant recovers.
Grade 4 Life-threatening; pressor or ventilator support indicated	SAR444245 infusion should be interrupted if applicable. If IRR is clearly attributable to SAR444245, SAR444245 should be permanently discontinued. The participant can continue treatment with the other anti-cancer therapy in combination During or after completion of infusion, additional appropriate medical therapy may include but is not limited to epinephrine ^b , IV fluids, antihistamines, NSAIDs, acetaminophen, narcotics, oxygen, vasopressors, corticosteroids. Increase monitoring of vital signs as medically indicated until the participant recovers.

a Information for preparation and storage of SAR444245 are provided in the pharmacy manual.

b In cases of anaphylaxis, epinephrine should be used immediately

Abbreviations: CTCAE = Common terminology criteria for adverse events; IRR = Infusion-related reaction; NCI = National Cancer Institute; NSAIDs: nonsteroidal anti-inflammatory drugs.

Participants who experience cetuximab-related infusion reactions should have cetuximab reduced according to [Table 7](#) and continue to receive antihistamine premedication prior to administration. Once the cetuximab infusion rate has been decreased due to an allergic/hypersensitivity reaction, it should remain decreased for all subsequent infusions. If the participant experiences a second infusion reaction at the decreased rate, cetuximab should be permanently discontinued. If any Grade 3-4 infusion reaction occurs, cetuximab treatment should be discontinued immediately.

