Severe infusion-related reactions, including anaphylactic reactions, may commonly occur, in some cases with fatal outcome. Occurrence of a severe infusion-related reaction requires immediate and permanent discontinuation of cetuximab therapy and may necessitate emergency treatment. Some of these reactions may be anaphylactic or anaphylactoid in nature or represent a cytokine release syndrome (CRS). Symptoms may occur during the first infusion and for up to several hours afterwards or with subsequent infusions.

Table 7 - Cetuximab infusion-related reaction dose modification and treatment guidelines

NCI CTCAE Grade	Dose modification
Grade 1 Mild reaction; infusion interruption not indicated; intervention not indicated	Decrease the cetuximab infusion rate by 50% and monitor closely for any worsening.
Grade 2 Requires therapy or infusion interruption but responds promptly to symptomatic treatment (eg, antihistamines, NSAIDs, narcotics, IV fluids); prophylactic medications indicated for ≤24 hrs	Stop cetuximab infusion and administer bronchodilators, oxygen, etc. as medically indicated. Resume infusion at 50% of previous rate once allergic/hypersensitivity reaction has resolved or decreased to Grade 1 in severity and monitor closely for any worsening.
Grades 3 or 4 Grade 3: Prolonged (ie, not rapidly responsive to symptomatic medication and/or brief interruption of infusion); recurrence of symptoms following initial improvement; hospitalization indicated for other clinical sequelae (eg, renal impairment, pulmonary infiltrates) Grade 4: Life-threatening; pressor or ventilator support indicated	Stop the cetuximab infusion immediately, administer epinephrine, bronchodilators, antihistamines, glucocorticoids, intravenous fluids, vasopressor agents, oxygen, etc., as medically indicated. Cetuximab should permanently discontinued. The participant can continue treatment with SAR444245.

Abbreviations: CTCAE = Common terminology criteria for adverse events; IRR = Infusion related reaction; NCI = National Cancer Institute.

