6.5.4.3 Fever, flu-like symptoms and cytokine-release syndrome (CRS)

Fever can frequently happen with infusion of IL-2 and may possibly evolve into flu-like symptoms or could be an early manifestation of CRS. Fever or flu-like symptoms should be graded according to CTCAE V5.0 and managed according to institutional standards.

Cetuximab may be associated with CRS. CRS typically occurs within one hour after infusion and is less commonly associated with bronchospasm and urticaria. CRS is normally most severe in relation to the first infusion of cetuximab. Cetuximab related IRR's, including CRS, are discussed in [Section 6.5.4.1](#). Please refer to [Table 7](#) for Cetuximab IRR dose modifications and treatment guidelines.

Cytokine-release syndrome should be graded as per American Society for Transplantation and Cellular Therapy (ASTCT) criteria integrated with central laboratory cytokine results, and managed per guidelines in [Table 8](#). If any grade of CRS is suspected, sites should make every effort to draw an additional blood sample for cytokines levels (by central laboratory) prior to the administration of tocilizumab, as well as C-reactive protein (CRP) and ferritin (by local laboratory).

Sites should have at least 2 full doses of tocilizumab available and access to an intensive care unit (ICU), in case participants develop CRS.

Guidelines for management of CRS according to severity grading are provided in [Table 8](#). ASTCT CRS consensus grading scale is provided in Section 10.11 of the master protocol.

Table 8 - Guidelines for the management of suspected cytokine release syndrome (CRS)

Event severity (ASTCT CRS Consensus Grading)	Recommended SAR444245 dose modification and supportive care guidelines	Recommended Cetuximab dose modifications and supportive care guidelines
Grade 1 
• Fever (Temperature $\geq 38^{\circ}\text{C}$)^b• No hypotension• No hypoxia	
No dose modification of SAR444245^a
 
Appropriate symptomatic treatment may include but is not limited to IV fluids (care should be taken to not excessively hydrate if evidence of vascular leak), antihistamines, NSAIDs and acetaminophen.
 
Close direct monitoring of the participant's clinical status. Clinical and laboratory monitoring should initially be performed daily, then less frequently as the participant improves.
	Decrease the cetuximab infusion rate by 50% and monitor closely for any worsening.

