Event severity (ASTCT CRS Consensus Grading)	Recommended SAR444245 dose modification and supportive care guidelines	Recommended Cetuximab dose modifications and supportive care guidelines
Grade 2	
 Fever^b (Temperature $\geq 38^{\circ}\text{C}$) Hypotension not requiring vasopressors and/or^c hypoxia requiring low-flow nasal cannula^d or blow-by. 
Temporarily interrupt SAR444245 if event occurs during infusion Additional appropriate medical therapy may include but is not limited to IV fluids (care should be taken to not excessively hydrate if evidence of vascular leak), antihistamines, NSAIDs and acetaminophen. Monitoring of vital signs, cardiac and other organ functions closely as medically indicated should be increased until the participant recovers. Transfer to ICU may be required. For participants with comorbidities, older age, or with oxygen requirement, hypotension, or participants in whom symptoms (eg, high grade fever) that do not respond to antipyretics within 72 hours treatment with corticosteroids and/or tocilizumab should be considered, as per guidance for Grade 3 events.
 
SAR444245 may be resumed when clinical symptoms have resolved or improved to Grade 1 and corticosteroid taper. No dose modification is required but decreasing to half the infusion rate can be considered.
	
Stop cetuximab infusion and administer bronchodilators, oxygen, etc., as medically indicated.
 
Resume infusion at 50% of previous rate once allergic/hypersensitivity reaction has resolved or decreased to Grade 1 in severity and monitor closely for any worsening.

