Infusion reactions	
Pembrolizumab
 
Common, but infusion-related reactions in labeling include drug hypersensitivity, anaphylactic reaction, anaphylactoid reaction, hypersensitivity and cytokine release syndrome.
 
Cetuximab
 
Severe infusion-related reactions, including anaphylactic reactions, may commonly occur, in some cases with fatal outcome. Symptoms may occur during the first infusion and for up to several hours afterwards or with subsequent infusions. Symptoms may include bronchospasm, urticaria, increase or decrease in blood pressure, loss of consciousness or shock. In rare cases, angina pectoris, myocardial infarction or cardiac arrest have been observed.
 
Anaphylactic reactions may occur as early as within a few minutes of the first infusion and can occur despite the use of premedication.
 
The risk for anaphylactic reactions is much increased in patients with a history of allergy to red meat or tick bites or positive results of tests for IgE antibodies against cetuximab (α-1-3-galactose). In these patients cetuximab should be administered only after a careful assessment of benefit/risk, including alternative treatments, and only under close supervision of well-trained personnel with resuscitation equipment ready.
 
A cytokine release syndrome (CRS) typically occurs within one hour after infusion and is less commonly associated with bronchospasm and urticaria. CRS is normally most severe in relation to the first infusion. Mild or moderate infusion-related reactions are very common comprising symptoms such as fever, chills, dizziness, or dyspnea that occur in a close temporal relationship mainly to the first cetuximab infusion
	
Pembrolizumab
 
Dose modification and treatment guidelines for pembrolizumab infusion associated reactions are provided in Table 5.
 
Cetuximab
 
Occurrence of a severe infusion-related reaction requires immediate and permanent discontinuation of cetuximab therapy and may necessitate emergency treatment.
 
It is recommended to warn patients of the possibility of such a late onset and instruct them to contact their physician if symptoms or signs of an infusion-related reaction occur.
 
The first dose should be administered slowly and the speed must not exceed 5 mg/min whilst all vital signs are closely monitored for at least two hours. If during the first infusion, an infusion-related reaction occurs within the first 15 minutes, the infusion should be stopped. A careful benefit/risk assessment should be undertaken including consideration whether the patient may have performed IgE antibodies before a subsequent infusion is given.
 
Premedicate with a histamine-1 (H1) receptor antagonist prior to cetuximab administration. Monitor patients for at least 1 hour following each cetuximab infusion, in a setting with resuscitation equipment and other agents necessary to treat anaphylaxis. Initiate SAR444245 infusion only when no infusion reaction has occurred after 1-2 hours of observation. In patients requiring treatment for infusion reactions, use recommended per the country-approved product labeling (eg, USPI, SmPC) for cetuximab.
 
If an infusion-related reaction develops later during the infusion or at a subsequent infusion further management will depend on its severity:

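### Cohort D2: the synopsis lets the first cetuximab infusion run faster than the 5 mg/min first-dose limit in Table 15, and Table 15 also conflicts with Table 7 on later Grade 2 infusion reactions

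*Protocol*

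**What the plan says.** **First-dose rate.** Substudy 04, Section 1.1 (Synopsis), gives the Cycle 1 Day 1 loading dose as 400 mg/m², "infused over 120 minutes (maximum infusion rate 10 mg/min, or as per local practice and labels". Later doses are 250 mg/m² over 60 minutes, also with a 10 mg/min maximum. Appendix 11 (Section 10.11), Table 15, lists among the cetuximab mitigations: "The first dose should be administered slowly and the speed must not exceed 5 mg/min". Section 4.3.3 and Table 3 repeat the doses but give no rate.

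**Background risk.** Section 2.3.1.2 says of cetuximab: "Approximately 90% of severe infusion reactions occurred with the first infusion despite premedication with antihistamines".

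**Reaction management.** Section 6.5.4.1 makes Table 7 the operative table: "Participants who experience cetuximab-related infusion reactions should have cetuximab reduced according to" Table 7. Section 6.5.4.3 also refers the reader to Table 7 "for Cetuximab IRR dose modifications and treatment guidelines". For Grade 2, Table 7 says: "Stop cetuximab infusion and administer bronchodilators, oxygen, etc. as medically indicated". The infusion then resumes at half the previous rate once the reaction has resolved or fallen to Grade 1. Table 8 has the same action for Grade 2 cytokine release syndrome: "Stop cetuximab infusion and administer bronchodilators, oxygen, etc., as medically indicated". Table 15 introduces its own graded list with "If an infusion-related reaction develops later during the infusion or at a subsequent infusion further management will depend on its severity", and at Grade 2 that list keeps a slow infusion going while symptoms are treated.

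**The concern.** Two parts of one substudy protocol give different rate limits for the same infusion. One is a dosing instruction with a fixed duration; the other is an unconditional safety limit. If the duration cannot be met within the limit for a participant of ordinary size, a site that uses the printed 120 minutes departs from a risk mitigation in its own protocol. Section 2.3.1 points to Table 15 for the mitigation strategies, and the benefit-risk conclusion in Section 2.3.3 relies on the measures taken to reduce risk, so the limit ought to appear in the dosing text.

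The Grade 2 conflict is of the same kind but matters less. A reader of Table 15 would continue an infusion that Table 7 says to stop.

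What is at stake is consistent first-dose safety handling. No effect on response rate or on any statistical figure follows from this point.

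**Working it through.** **Inputs.** Loading dose 400 mg/m², duration 120 minutes and maximum 10 mg/min, from the Substudy 04 synopsis. First-dose limit 5 mg/min, from Table 15. Body surface area (BSA) is not given in the protocol, so a range is assumed. The protocol states no mean rate, so there is no figure to reproduce.

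**Formulas.**
- Mean rate over 120 minutes = 400 × BSA / 120 = 3.33 × BSA mg/min.
- BSA at which this equals 5 mg/min: 5 × 120 / 400 = 1.50 m².
- BSA at which the 10 mg/min maximum begins to bind at 120 minutes: 10 × 120 / 400 = 3.00 m².
- Shortest compliant duration at 5 mg/min = 400 × BSA / 5 = 80 × BSA minutes.

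**Results.**

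| Assumed BSA (m²) | Dose (mg) | Mean rate over 120 min (mg/min) | Relative to 5 mg/min | Minutes needed at 5 mg/min | Added to 120 min |
|---|---|---|---|---|---|
| 1.4 | 560 | 4.67 | −6.7% | 112 | none |
| 1.5 | 600 | 5.00 | 0% | 120 | none |
| 1.6 | 640 | 5.33 | +6.7% | 128 | 8 |
| 1.8 | 720 | 6.00 | +20.0% | 144 | 24 |
| 2.0 | 800 | 6.67 | +33.3% | 160 | 40 |
| 2.2 | 880 | 7.33 | +46.7% | 176 | 56 |

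The 1.5 m² threshold uses printed numbers only. Above it the mean rate itself is over 5 mg/min, so no infusion profile can both finish in 120 minutes and keep to the Table 15 limit. The synopsis maximum does not help, because at 120 minutes it has no effect below 3.0 m².

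**Grade 2 reactions, side by side.** These apply after the first 15 minutes of the first infusion, or at a later infusion.
- Table 15: carry on slowly and treat.
- Table 7: stop, then restart at half rate once resolved or Grade 1.
- Table 8, for Grade 2 cytokine release syndrome: stop, with the same restart.

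For Grades 3 and 4, Tables 7 and 15 both stop the infusion and end cetuximab. A later Grade 1 reaction is broadly compatible, with a slow infusion in one and a halved rate in the other.

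**The case against.** The strongest reply is that the synopsis itself defers to local practice and labels. A site whose label requires 5 mg/min follows the synopsis by using it. Cetuximab is sourced locally where possible, Section 2.3.1.2 sends the reader to country labeling, and Table 15 reads in part as a summary of label information. Section 6.1.1 says preparation and administration are detailed in the pharmacy manual, which is not shown, and part of the Cohort D2 dosing text is redacted. All of this stands as a limit on what can be said about practice. A reader might infer that every participant above 1.5 m² will be infused too fast; the documents do not support that. They do support a conflict in the printed text: the synopsis permits a slower rate without requiring it, and Table 15 states its limit with no local exception.

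A second reply is that the 90% figure may not carry over. Section 2.2.3 describes the Cohort D2 population as having already had cetuximab, for whom Cycle 1 Day 1 is a re-exposure. That is fair. But criterion I 04 in Section 5.1 accepts prior bevacizumab and/or cetuximab, so cetuximab-naive participants can enrol, and the figure applies most directly to them. The protocol also gives no evidence of how much risk changes between 5 and 6 mg/min.

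Two further inferences should be resisted.
- **A count of affected participants.** Section 2.3.1.2 gives infusion reactions in 8.4% of patients, with Grades 3 and 4 in 2.2%. One could compute 8.4% − 2.2% = 6.2%, or 40 × 0.062 = 2.5 participants, as a ceiling for the reaction conflict. It is not a ceiling: those are rates from cetuximab trials, and Section 2.3.1.3 says reactions may be more frequent and more severe in combination with SAR444245.
- **An early-stop rule missing from Table 7.** Table 15 stops the first infusion for any reaction in its first 15 minutes, while Table 7 only halves the rate at Grade 1. However, Table 7 defines Grade 1 as a reaction for which interruption is not indicated, which softens the difference. Adding the rule to Table 7 without a restart rule could leave a participant with a partial loading dose, and Section 6.5.2 does not allow the 400 mg/m² dose to be repeated after a delay.

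**Conclusion.** The rate contradiction is real and should be corrected. Used as printed, the 120-minute duration exceeds the Table 15 first-dose limit above exactly 1.5 m². The excess is 7% to 47% for an assumed BSA of 1.6 to 2.2 m², and 20% at 1.8 m². The threshold rests on printed figures alone; the percentages rest on the assumed BSA values. How often sites would exceed the limit cannot be determined from the documents.

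The Grade 2 conflict is also real but secondary, because Sections 6.5.4.1 and 6.5.4.3 direct sites to Table 7.

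**What to change.** **Synopsis, Cohort D2 cetuximab regimen.** Change the first-dose text to: Cycle 1 Day 1, 400 mg/m² over at least 120 minutes, not exceeding 5 mg/min, or slower if the local label requires. Leave later doses unchanged. Check that the pharmacy manual says the same.

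**Table 15.** Replace the cetuximab list by grade (a to c) with a reference to Table 7, just as Table 15 already refers to Table 5 for pembrolizumab. Leave Table 7 as it is.

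**Cost.** Two wording edits in Substudy 04. The first infusion becomes about 8 to 56 minutes longer at an assumed 1.6 to 2.2 m² (24 minutes at 1.8 m²), on Cycle 1 Day 1 only; at 1.5 m² or below nothing is added to the 120 minutes. No extra participants, visits or assessments are needed.
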